4.4. Treatments

4.4.1. Treatments Administered

Eight treatment arms administering various combinations of mRNA-1273 and mRNA-1273.351 (Table 1).

Summary of Treatment Arms:

- 2A: Evaluates the mRNA-1273 EUA vaccination series, plus a variant vaccine as a third dose.
- 2B: Evaluates a 50-mcg mRNA-1273 vaccination series, plus a variant vaccine as a third dose.
- 2C: Evaluate 2 doses of the homologous variant vaccine at 100mcg.
- 2D: Evaluate 2 doses of the homologous variant vaccine at 50mcg.
- 2E: Evaluate heterologous prime-boost strategies at 100mcg.
- 2F: Evaluate heterologous prime-boost strategies at 50mcg.
- 2G: Evaluate a 1:1 mix of vaccine (2 doses), with the total dose for both vaccines equal to 100 mcg.
- 2H: Evaluate a 1:1 mix of vaccine (2 doses), with the total dose for both vaccines equal to 50 mcg.

4.4.2. Identity of Investigational Product(s)**Product: There are two clinical presentations of mRNA-1273 — mRNA-1273 and mRNA-1273.351**

mRNA-1273 (0.2 mg/mL) is an LNP dispersion containing an mRNA that encodes for the prefusion stabilized S protein of the Wuhan-Hu-1 strain of SARS-CoV-2. mRNA-1273 consists of an mRNA Drug Substance that is manufactured into LNPs composed of the proprietary ionizable lipid, SM-102, and 3 commercially available lipids, cholesterol, 1,2-distearoyl-sn-glycero-3-phosphocholine (DSPC), and PEG2000 DMG.

mRNA-1273.351 (0.5 mg/mL) is formulated in the same way but contains mRNA that encodes for the prefusion stabilized S protein of the B.1.351 variant SARS-CoV-2 strain.

4.4.3. Method of Assigning Subjects to Treatment Groups (Randomization)

Subjects in Cohort 2 will be randomized in a ratio of 3:3:4:4:4:4:4 to Arms 2A-H. Randomization will be done in the SDCC's Advantage eClinicalSM (Electronic Data Capture System).

4.4.4. Selection of Dose in the Study

See Section 4.2 for a discussion of dose selection for this study.

4.4.5. Prior and Concomitant Therapy

Concomitant medications include only prescription medications and vaccines received outside of the study taken by the subject at the time of enrollment through 28 days after the last vaccination. At each study visit, if there are new SAEs, Protocol Specified AESIs, MAAEs, or NOCMCs, concomitant medications should be recorded on the appropriate DCF.

4.4.6. Treatment Compliance

All subjects are to receive 2 (Arms 2C-H) or 3 (Arms 2A-B) doses of study product administered in the clinic. The number of doses received will be reported in [Table 7](#) (Arms 2A-B) and [Table 8](#) (Arms 2C-H).

5. SAMPLE SIZE CONSIDERATIONS

Rare AEs are not demonstrable in a clinical study of this size; however, the probabilities of observing one or more AEs given various true event rates are presented in [Table 4](#). With the assumption that all enrolled subjects will likely complete immunizations and safety visits in this relatively short duration study, the following statistical considerations apply. With 15 subjects in Arms 2A and 2B, the chance of observing at least one AE of probability 20% or more is approximately 97%. Therefore, if no AEs of a given type occur in Arms 2A or 2B, we can be relatively confident that they will occur in fewer than 20% of people once the vaccine is implemented. With 20 subjects in each arm (Arms 2C-2H), the chance of observing at least one AE of probability 20% or more is approximately 99%. Therefore, if no AEs of a given type occur in Arms 2C-2H, we can be relatively confident that they will occur in fewer than 20% of people once the vaccine is implemented. With approximately 150 subjects across these eight Arms (2A-2H), the chance of observing at least one AE of probability 3% or more is at least 99%. Therefore, if no AEs of a given type occur across Cohort 2, we can be very confident that any dosage/combination independent event will occur in fewer than 3% of people once the vaccine is implemented.

6. GENERAL STATISTICAL CONSIDERATIONS

6.1. General Principles

In general, continuous variables will be summarized using the following descriptive statistics: n (non-missing sample size), mean, standard deviation, median, maximum, and minimum. The frequency and percentages (based on the non-missing sample size) of observed levels will be reported for all categorical measures. In general, all data will be listed, sorted by site, treatment, and subject, and when appropriate by visit number within subject. All summary tables will be structured with a column for each treatment and will be annotated with the total population size relevant to that table/cohort, including any missing observations.

6.2. Analysis Populations

6.2.1. Safety Population

The Safety Analysis population includes all subjects who received one dose of the vaccine.

6.2.2. Modified Intent-to Treat Population

The modified intent-to-treat (mITT) population includes all subjects who received at least one dose of the vaccine and contributed both pre- and at least one post-vaccination venous blood samples for immunogenicity testing for which valid results were reported.

6.2.3. Per Protocol Population

In the final analysis, protocol deviations will be reviewed to determine which protocol deviations may affect the analysis. The per protocol (PP) population will then be defined – and this includes all subjects in the mITT subset with the following exclusions:

- Data from all available visits for subjects found to be ineligible at baseline.
- Data from all visits subsequent for the protocol deviations that are considered to affect the science.
- Data from any visit that occurs substantially out of window.

6.3. Covariates and Subgroups

The protocol does not define any formal subgroup analyses, and the study is not adequately powered to perform subgroup analyses.

6.4. Missing Data

There are no imputations planned for missing data.

For immunogenicity assays, any values below the lower limit of detection will be imputed as one-half the lower limit of detection for analysis purposes. Any such imputations will be noted in the corresponding analysis.

6.5. Interim Analyses and Data Monitoring

Cumulative safety information, study status, and primary endpoint results may be published, presented at a public forum, or presented as summaries aggregated by study arm at the discretion of the sponsor while the study is ongoing. Any ad-hoc analyses, jointly developed by the SDCC and/or the Vaccine Research Center (VRC), other participating laboratories and ModernaTX, Inc., will be executed by the SDCC as needed. None of the interim analyses will include any formal statistical hypothesis testing; therefore, p-value adjustment will not be made to any analyses.

The SMC will not need to meet (unless halting rules are met), and materials will be provided electronically. Documentation of review and any concerns noted will be solicited electronically. The SMC will review cumulative AE data after all subjects in Cohort 1 have been dosed and completed Day 8.

Interim data review of immunogenicity may be performed to inform public health decisions.

Statistical analyses of secondary immunogenicity endpoints, by vaccine schedule group, may be performed when subjects have completed key immunogenicity visits. Immunogenicity reviews may be shared with the SMC, as determined by DMID.

Data may be disseminated to public health officials and partners as needed and included in publications and presentations to inform the global scientific community.

Interim analyses of safety, reactogenicity, and immunologic response data may be done, as needed.

6.6. Multicenter Studies

Data will be pooled across all clinical sites. Center effects are not anticipated because the sites are using standardized procedures for vaccination and assessment of solicited and unsolicited adverse events, and the study relies on central laboratories for the assessment of immunogenicity endpoints.

6.7. Multiple Comparisons/Multiplicity

There are no adjustments planned for multiple comparisons.

7. STUDY SUBJECTS

7.1. Disposition of Subjects

[Table 11](#) will present a summary of the reasons that subjects were screened but not enrolled.

The composition of analysis populations, including reasons for subject exclusion, by treatment arm, is presented in [Table 9](#) and [Table 10](#).

The disposition of subjects in the study will be tabulated by treatment group ([Table 7](#) and [Table 8](#)). The tables show the total number of subjects screened, enrolled, receiving the first vaccination, receiving second vaccination, receiving third vaccination (Arms 2A-B), terminated from study follow-up, and the number completing the study.

A flowchart showing the disposition of study subjects, adapted from the Consort Statement [5] will be included ([Figure 1](#)). This figure will present the number of subjects screened, enrolled, lost to follow-up, and analyzed, by treatment group.

A listing of subjects who discontinued dosing or terminated from study follow-up and the reason will be included in [Listing 2](#).

7.2. Protocol Deviations

A summary of subject-specific protocol deviations will be presented by the reason for the deviation, the deviation category, and treatment group for all subjects ([Table 5](#)) as well as similar summaries for major subject-specific protocol deviations ([Table 6](#)). All subject-specific protocol deviations and non-subject specific protocol deviations will be included in [Appendix 3](#) as data listings ([Listing 3](#) and [Listing 4](#), respectively).

8. IMMUNOGENICITY EVALUATION

8.1. Primary Immunogenicity Analysis

See Section 9 for safety analyses which are the primary endpoints of this study.

8.2. Secondary Immunogenicity Analyses

Summaries and analysis of immunogenicity data will be presented for the mITT population. If there are protocol deviations which may affect the analysis, a per-protocol (PP) analysis may also be performed.

Seropositive is defined as above LLOD (if available).

Binding will be measured by three types of ECLIA assays. The first is a single-plex (ECLIA) that produces arbitrary units/mL that is a validated assay and can be converted to binding antibody units for Wa-1 S-2P binding. The second is a 4-plex (ECLIAv2) assay that is also validated and produces arbitrary units/mL to measure variant specific binding. The final assay is a 10-plex (ECLIAv2) that is a fit for purpose assay that produces area under the curve and is used to assess binding for variants of concern.

Seropositive rates, geometric mean fold rise (GMFR) and geometric mean (GM) or Williams mean of arbitrary units per mL (AU/mL), binding antibody unit/mL (BAU, only for Wa-1 [S2-P] variant), and AUC for SARS-CoV-2 will be calculated at Study Days 1 (GM only), 15, 29, 43, 57, 71, 85, 147, 237, and 422 (Arms 2A-B) and Days 1, 15, 29, 43, 57, 119, 209, 394 (Arms 2C-H) by treatment group and will include both tabular and graphical summaries. Seropositive rates, GMFR, and GM will be presented with their corresponding 95% confidence interval (CI) estimates (using Student's t-distribution for GM and GMFR and the Clopper-Pearson binomial method for seropositive) at each post vaccination timepoint and overall peak GM. Summaries of GM are included starting with Table 15 and ending with Table 62; and summaries of GMFR and seroconversion are included starting with Table 191 and ending with Table 238. Graphical displays will include reverse cumulative distribution plots (starting with Figure 2, ending with Figure 25; and starting with Figure 86, ending with Figure 109), individual values over time (starting with Figure 170, ending with Figure 193; and starting with Figure 254, ending with Figure 277), geometric mean over time (starting with Figure 338, ending with Figure 361; and starting with Figure 422, ending with Figure 445), and distribution of responses over time (starting with Figure 506, ending with Figure 529; and starting with Figure 590, ending with Figure 613).

Neutralization assays using SARS-CoV-2 pseudovirus neutralization assay (PsVNA) and focus reduction neutralization test (FRNT) will be run using serial dilutions against available variants (e.g., Beta, Delta, Omicron). ID₅₀ and ID₈₀ will be calculated using methodology such as a 5-parameter logistic regression model by the laboratory. ID₅₀ and ID₈₀ will be summarized by group using the geometric mean and 95% CI (using Student's t-distribution) at each post vaccination timepoint and overall peak GM (starting with Table 63 and ending with Table 182). Summaries of GMFR and seropositive are included starting with Table 239 and ending with Table 358. The ratio of the result for each variant divided by the result of the D614G variant will be calculated and summarized as the geometric mean ratio (GMR) (starting with Table 359 and ending with Table 382). Graphical displays for PsVNA and FRNT will include reverse

cumulative distribution plots (starting with [Figure 26](#), ending with [Figure 85](#); and starting with [Figure 110](#), ending with [Figure 169](#)), individual values over time (starting with [Figure 194](#), ending with [Figure 253](#); and starting with [Figure 278](#), ending with [Figure 337](#)), geometric mean over time (starting with [Figure 362](#), ending with [Figure 421](#); and starting with [Figure 446](#), ending with [Figure 505](#)) and distributions of responses over time (starting with [Figure 530](#), ending with [Figure 589](#); and starting with [Figure 614](#), ending with [Figure 673](#)).

Correlations between all assays will be displayed in a heatmap (starting with [Figure 674](#) and ending with [Figure 697](#)).

Summaries of N-antibody expression status and self-reported infection status will be reported in [Table 383](#), [Table 384](#), [Table 385](#), and [Table 386](#).

Individual immunogenicity responses are shown in [Listing 8](#).

Any additional variants of concern not listed in the appendices that are of scientific interest may be analyzed in an analogous manner in the final report.

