3. STUDY OBJECTIVES AND ENDPOINTS

3.1. Study Objectives and Endpoints

| OBJECTIVES | ENDPOINTS (OUTCOME MEASURES) |
|--|--|
| Primary | |
| 
 To evaluate the safety and reactogenicity of mRNA-1273 and mRNA-1273.351 vaccines, in naïve individuals. | 
 Frequency and grade of each solicited local and systemic reactogenicity AE during a 7-day follow-up period post each vaccination. Frequency and grade of any unsolicited AEs during the 28-day follow-up period post each vaccination. Frequency of any SAEs, Protocol Specified AESIs, NOCMCs, and MAAEs from the first vaccination through 12 months after the last vaccination. |
| Secondary | |
| 
 To assess humoral immunogenicity of mRNA-1273 and mRNA-1273.351 vaccines, in naïve individuals. | 
 Response rate, and magnitude of SARS-CoV-2-specific antibody binding and neutralization titers in serum samples as assessed via a range of assays at all timepoints. |
| Exploratory | |
| 
 To assess, in at least a subset of samples the innate immune response and B cell response following vaccination. | 
 Magnitude, phenotype, and percentage of innate immune cells and SARS-CoV-2 specific B cells, as measured by flow cytometry, and targeted B cell repertoire analysis at different timepoints post vaccination relative to baseline. |
| 
 To assess, in at least a subset of samples, the SARS-CoV-2 S protein-specific T cell responses. | 
 Magnitude, phenotype, and percentage of cytokine producing S protein-specific T cells, as measured by flow cytometry at different timepoints post vaccination relative to baseline. |

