3.2. Study Definitions and Derived Variables

For calculations using the baseline value, the value obtained pre-first vaccination (Day 1) will be used. For samples with an AUC of zero at baseline, fold-rise will be calculated by dividing the post-vaccination result by the lowest reported value. AUC is calculated using the trapezoidal method applied to a serial dilution curve.

The Williams mean is a variation of the geometric mean using $\log(1+x)$ transformation of the data, where x is each data point. The Williams mean is used in cases where 0 is a possible and/or reported value of the data.

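### The antibody response rate is defined without reference to Day 1, its table shells have no Day 1 row, and the binding tables carry three unreconciled labels for it

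*SAP*

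**What the plan says.** Section 3.1 of the SAP gives the secondary endpoint as "Response rate, and magnitude of SARS-CoV-2-specific antibody binding and neutralization titers in serum samples as assessed via a range of assays at all timepoints". Section 8.2 supplies the only cut-off for a rate: "Seropositive is defined as above LLOD (if available". It is applied visit by visit.

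On timing, section 8.2 treats the two sets of arms differently. For the three-dose arms, the rates, fold rises and means "will be calculated at Study Days 1 (GM only), 15, 29, 43, 57, 71, 85, 147, 237, and 422 (Arms 2A-B"; on Day 1 only the geometric mean is planned. For the two-dose arms it lists "Days 1, 15, 29, 43, 57, 119, 209, 394 (Arms 2C-H" without that limit. It then says that the estimates are shown with confidence intervals "at each post vaccination timepoint and overall peak GM".

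The printed shells that carry the seropositive percentage are Tables 191, 215, 239, 263, 287 and 323. All six begin at Day 15.

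The naming also varies. The text of section 8.2 describes Tables 191-238 as showing seroconversion. Tables 216-238 are titled as 4-fold rise. The Table 215 shell, whose format they follow, prints a seropositive percentage. Neither seroconversion nor 4-fold rise is defined.

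For the 10-plex binding assay, which reports an area under the curve, section 3.2 expects zeros: "For samples with an AUC of zero at baseline, fold-rise will be calculated by dividing the post-vaccination result by the lowest reported value". No cut-off for positivity on that scale is given beyond the conditional one in section 8.2.

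**The concern.** A response rate should say how many subjects responded to vaccination. The share above a detection limit at a visit says how many have detectable antibody, whatever its origin. The two agree only if nobody is above the limit on Day 1, or if everyone responds.

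The entry criteria do not rule out reactivity on Day 1. Exclusion criterion 18 removes Cohort 2 subjects with a known positive serologic test, and the schedules in Tables 2 and 3 list no screening serology. Table 12 has a row for baseline N-antibody positives. The mITT population requires a valid Day 1 result but does not remove positives. An unrecognised positive breaches no entry criterion, so the per-protocol exclusion for ineligibility would not remove it either.

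At stake is whether one of the two secondary humoral measures can be read as an effect of the vaccine. This matters most where true response is low: Day 15, heterologous variants and late visits. Cross-protective responses are the stated purpose of Cohort 2.

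**Working it through.** The SAP gives no target or precision for this rate, so there is no figure of its own to reproduce.

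**1. Day 1 across the outputs.** The geometric mean shells (for example Tables 15, 39 and 63) have a Day 1 row. The exploratory T-cell shells (Tables 183 and 185) have a Day 1 response rate with an exact interval. The N-antibody shells (Tables 383 and 385) have a Day 1 percentage positive. The seropositivity shells have none, in any arm. For Arms 2A-B this follows the text; for Arms 2C-H it conflicts with the visit list in the text.

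**2. Size of the effect.** Inputs: b, the share above the limit on Day 1 (not in the SAP; assumed 5%, 10% and 20%, and assumed to stay above it); p, conversion among those at or below the limit on Day 1.

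Reported rate = b + (1-b)p. Excess over p = b(1-p).

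| p | b = 5% | b = 10% | b = 20% | excess, points |
|---|---|---|---|---|
| 20% | 24% | 28% | 36% | 4 to 16 |
| 50% | 52.5% | 55% | 60% | 2.5 to 10 |
| 80% | 81% | 82% | 84% | 1 to 4 |
| 100% | 100% | 100% | 100% | 0 |

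**3. Illustration in counts.** Take an arm of 20 with 10 new conversions (assumed counts, Clopper-Pearson intervals as the SAP specifies).

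- 2 subjects above the limit on Day 1: the SAP rate is 12/20 = 60% (36.1 to 80.9), against 10/18 = 55.6% (30.8 to 78.5) among Day 1 negatives.
- 4 such subjects: 14/20 = 70% (45.7 to 88.1), against 10/16 = 62.5% (35.4 to 84.8).

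**4. Chance that an arm is affected.** The probability of at least one Day 1 positive is 1-(1-b)^n, the formula behind Table 4. For n = 15 and n = 20 it is 53.7% and 64.2% at b = 5%, and 96.5% and 98.8% at b = 20%.

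**5. The labels give different rates.** A 4-fold rise is measured from Day 1, so a subject already above the limit does not qualify automatically. It also differs for Day 1 negatives. Section 6.4 sets results below the limit to half of it, so a 4-fold rise needs at least 4 × 0.5 = 2 times the limit, while seropositivity needs only a result above it.

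**The case against.** Four arguments carry weight.

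First, a reader might infer that Day 1 positives cannot be seen at all. That goes too far. Listing 8 and the plots of individual values over time show them by subject. Day 1 geometric means, Table 12 and Tables 383-386 show them in part. N-antibody marks past infection, so it would miss spike binding from assay background or cross-reaction, but the individual values should show it. What is missing is the Day 1 percentage in the tables that report the endpoint.

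Second, a reader might infer that the text excludes Day 1 everywhere, or that the problem is the same whichever label applies. Neither is supported. The restriction to the geometric mean is written for Arms 2A-B only. A true 4-fold rise would refer to Day 1 and would largely remove the difficulty for Tables 216-238, 23 of the 24 binding fold-rise tables for Arms 2C-H. But it is undefined there, the shell prints something else, and the binding tables for Arms 2A-B and all the neutralization tables (239-358) are titled as seropositivity.

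Third, a reader might infer that each Day 1 positive adds a full 6.7 points (1/15) or 5 points (1/20). That holds only at p = 0. One in 20 is b = 5%, which adds 4 points at p = 20% and 1 point at p = 80%.

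Fourth, the effect may be small. Section 4.2 cites 100% neutralizing seroconversion at 14 and 28 days after the second dose of mRNA-1273; at that level the excess is zero. Cohort 2 has no known prior infection, the planned outputs are descriptive, and no multiplicity adjustment or interim hypothesis test depends on them. This stands for peak visits. It does not settle Day 15, heterologous variants or late visits.

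**Conclusion.** The point holds in a limited form. The rate offered for the response-rate endpoint has no baseline condition, its shells omit Day 1 in every arm, and the binding outputs have three names that imply different calculations. For the 10-plex assay the cut-off may not exist, and no rule says what to report then. In the table list that assay is the only binding assay for B.1.617.2, P.1, B.1.1.7 and B.1.1.529.

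The size is b(1-p), so it is material where few Day 1 negatives convert and negligible where nearly all do. The ranges rest on an assumed b of 5% to 20%, for which the SAP gives no source, and on Day 1 positives staying above the limit. The Positive row in an empty Table 12 shell shows that the plan allows for baseline positives; it does not show that any number is expected. Nor can the SAP settle whether the detection limit is a poor boundary between negative and positive sera, because it gives neither the limits nor their derivation.

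**What to change.** In section 8.2 and the shells:

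- Tabulate seropositivity on Day 1 for all eight arms, and make the visit lists for Arms 2A-B and 2C-H agree on this.
- State one definition of response against Day 1. One workable form is above the limit for subjects at or below it on Day 1, and at least a 4-fold rise for the others.
- Use that definition in the text and in Tables 191-358, and align the titles, so that seroconversion, 4-fold rise and seropositive no longer stand for one another.
- Omit the seropositive row for any 10-plex antigen that has no detection limit, and say so in a footnote.

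The cost is SAP wording, retitling and one row per table. No new samples or assays are needed, because Day 1 results are already required for the geometric means and fold rises. The downside is that some early response rates will be slightly lower.
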